### **3.2 Exclusion Criteria (08-06-2013)**

- 3.2.1** Retroareolar breast cancer lesions within one cm. depth from the skin surface.
- 3.2.2** Concomitant or history of nipple discharge or skin involvement.
- 3.2.3** Patient with distant metastases.
- 3.2.4** Patient with extensive intraductal carcinoma.
- 3.2.5** Any previously irradiated ipsilateral breast cancer.
- 3.2.6** Patients with Paget's disease of the nipple.
- 3.2.7** Patients with collagenous diseases, as systemic lupus erythematosis, scleroderma or dermatomyositis.
- 3.2.8** Other malignancy, except non-melanomatous skin cancer, less than 5 years prior to participation in this study.
- 3.2.9** Patients who are pregnant or lactating due to potential exposure of the fetus to RT and unknown effects of RT to lactating females.
- 3.2.10** Positive surgical margins following nipple sparing mastectomy

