### **5.2 Intraoperative parameters**

Intraoperative events and findings will be reported as routinely done in the operative report. Pathologic examination of the frozen section of the tissue underneath the NAC will be performed at the time of surgical procedure and results will be recorded in the study records. If pathology is positive, the patient will be taken off the study as screen failure.

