### **5.4 Pathologic evaluation of specimens**

Pathologic examination of the frozen section of the tissue underneath the NAC will be performed at the time of surgical procedure and results will be recorded in the study records. If pathology is positive, the patient will be taken off the study as screen failure. If pathology is negative, the surgeon will then perform a Skin Sparing Mastectomy, sparing the NAC. If the patient's NAC tissue biopsy is negative by frozen, but positive after standard hematoxylin and eosin, the patient will be taken off the study and the discussion will be done with the patient about options of removal of the NAC or postoperative irradiation of NAC outside the protocol.

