## 9.0 DATA REPORTING

Basic forms include

- On-study information, including patient eligibility data and patient history
- Flow-sheets, tumor/disease assessment forms or other forms for interim monitoring
- Specialty forms for pathology, radiation or surgery
- Off-study summary sheet, including a final assessment by the treating physician
- Follow-up forms when required.

The following can be used for the location if using SCCC forms.

Data must be submitted according to the protocol requirements for ALL patients registered. Patients for whom documentation is inadequate to determine eligibility will generally be deemed ineligible.

A list of forms to be submitted, as well as expectation dates, is found in Appendix IV.

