## 10.0 STATISTICAL CONSIDERATIONS

### 10.1 Study Size

For the purpose of dose escalation of NAC-radiation treatment, **evaluable patients** will be defined as any eligible patient that begins NAC irradiation treatment. However to evaluate feasibility of the NAC-sparing mastectomy with reconstruction, any patient who undergo surgery will be considered evaluable.

Following the dose escalation/de-escalation procedure described in section 4.2, we anticipate that 12 to 18 evaluable patients will be enrolled in this phase I study *during the dose-finding part*. The **number of evaluable patients** that will be needed depends on the number of times the NAC-radiation dose is escalated or possibly de-escalated. If the escalation occurs from dose level II up to dose level IV, between 14-18 evaluable patients will be required. If the dose is de-escalated after dose level II been evaluated in 6 patients, then 12 evaluable patients will be required, assuming 6 patients would be evaluated at dose level I. With 6 evaluable patients, the probability of not escalating when the true DLT rate is 35% is 68%. If the true DLT rate is 20%, the probability that the dose will be escalated is 66%.

A maximum of 6 patients per year is expected to be enrolled, since each patient must be evaluated for a minimum of 35 days and at most two patients will be enrolled simultaneously (within < 30 days after completion of the 5 days NAC radiation treatment). Thus, the expected accrual period is between 2-3 years.

An **additional expansion cohort of 12 patients** will be enrolled at the “**potential**” **recommended phase II dose (RP2D)** over an expected accrual period of 2 years.

To gather data on recurrence and survival, all patients will be followed at their clinic visits as clinically indicated.

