## 10.2 Planned Analysis

**Patient demographics** (age, race/ethnicity), **laboratory parameters, disease characteristics** (such as, tumor stage, grade), will be summarized using descriptive statistics: counts and percentages, range, median, mean, and standard deviation, as appropriate [23].

**Toxicities** resulting from radiation treatment will be tabulated by type, grade, duration, and attribution to treatment according to NCI CTCAE version 3.0, and by administered NAC radiation dose. A patient-level summary by worst grade toxicity will be included. Any grade 3, 4 or 5 or unexpected lower grade toxicities will be reported.

**Intraoperative parameters and perioperative parameters** (complications, events, and findings) will be described in the operative report as routinely done.

**Surgery success rate**, defined as the proportion of patients who had successful NAC sparing surgery with reconstruction divided by the total number of study patients, will be determined.

**Cosmetic results** will be assessed by both the physician(s) and the patients at 3, 6 and 12 months, using a 4-category ordinal scale (excellent, good, fair, and poor). Data will be summarized in terms of number and % of patients in these 4 possible categories at those assessment times separately for assessment by physician and by patient. Statistical analysis methods for contingency tables will be used to compare changes over time for each evaluator (physician or patient), and also to compare agreement between physician and patient assessment at a given time. [24]

To gather data on recurrence and survival, all patients will be under follow-up for a minimum of 5 years, unless they withdraw consent or die within that time.

Given the small study size and the expected low incidence of recurrence, we do not expect any such recurrences within 5 years. However, if patients do recur, the **number of recurrences** will be reported, along with corresponding summary regarding time to recurrence, type of recurrence -- local (ipsilateral nipple-areola recurrence in-field, peripheral, or extra-field location) or distant, irradiated volume, and radiation dose. If the number of events allows, **disease-free survival and overall survival** will be estimated by the Kaplan-Meier method. [25]

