## 11.5 RECORDING AND PROCESSING OF DATA

If using hard copies of CRF's, study center personnel will complete individual CRF's in black ink. All corrections to entered data will be made by drawing a single line through the information to be corrected without obscuring it. All corrections will be initialed, dated and explained, if necessary. **Do not use “white-out” or obscuring correction tape.** A CRF is required for every patient who received any amount of study treatment. The investigator will ensure that the CRF's are accurate, complete, legible and timely. Separate source records are required to support all CRF entries.

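### Does the surgery success rate lose patients with a positive frozen section from its denominator and so come out too high?

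*Combined protocol and SAP*

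**What the plan says.** Section 10.2 (Planned Analysis) introduces the surgery success rate, "defined as the proportion of patients who had successful NAC sparing surgery with reconstruction divided by the total number of study patients". It defines neither the denominator term nor success, and it does not point to another section.

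Section 10.1 (Study Size) names two evaluable sets. For dose escalation, the set is eligible patients who start NAC irradiation. For the feasibility of NAC-sparing mastectomy with reconstruction, "any patient who undergo surgery will be considered evaluable".

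Three other places remove patients on findings made at or after the operation:

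- Sections 5.2 and 5.4, on the intraoperative frozen section: "If pathology is positive, the patient will be taken off the study as screen failure". Section 5.4 adds: "If pathology is negative, the surgeon will then perform a Skin Sparing Mastectomy, sparing the NAC".
- Section 5.4, on a patient negative on frozen section but positive on permanent section: "the patient will be taken off the study and the discussion will be done with the patient about options". The screen-failure label is not used here.
- Section 3.2.10 lists as an exclusion: "Positive surgical margins following nipple sparing mastectomy".

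On data capture, section 9.0 says "Data must be submitted according to the protocol requirements for ALL patients registered", and section 11.5 says "A CRF is required for every patient who received any amount of study treatment".

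**The concern.** A patient with a positive frozen section has consented before surgery (section 3.1.14 and the Appendix I calendar) and is already under anaesthesia when declared a screen failure. Under sections 4.1.1 and 5.4 the NAC is spared only after a negative frozen section, so this patient cannot be a success. Someone reading 10.2 beside 5.2 could decide that a screen failure is not a study patient and drop her. Only non-successes would be dropped, so the rate could only rise.

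This is the one rate in 10.2 that says how often NAC-sparing surgery with reconstruction is achieved. It bears on the technical-feasibility part of the first hypothesis and on the secondary objective of describing the surgery. Two analysts could report different figures from the same patients.

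**Working it through.** **No figure to reproduce.** The documents give no expected success rate, target or interval for this measure, and no expected share of positive frozen sections.

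**Step 1: which population governs.** Section 10.1 assigns a population to surgical feasibility and contrasts it with the irradiated set used for dose finding. Sections 5.2 and 5.4 deal with what happens to the patient; neither mentions an analysis set. Of these sections, only 10.1 addresses the analysis question.

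**Step 2: has a frozen-positive patient had surgery?** Section 4.1.1 places the frozen section under the heading Surgery. Section 5.2 places it within the operation. Section 6.1.2 says it lengthens the anaesthetic by about half an hour. In the ordinary sense she has undergone surgery and is evaluable under 10.1.

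**Step 3: size if the label were carried over.** Let f be the share of operated patients with a positive frozen section and s the success rate among the rest.

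- Rate over all operated patients: s(1 − f)
- Rate with frozen-positive patients removed: s
- Upward shift: s − s(1 − f) = s·f

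Illustrative inputs: f = 5.6% and 12% are occult NAC involvement in mastectomy specimens (section 1.1), and f = 2% is an assumption. The planned size is 12 + 12 = 24 to 18 + 12 = 30. Number operated = number remaining/(1 − f), rounded.

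| Remaining | f | Operated | Rate if removed, s = 100% | Rate over all operated | Shift (points) |
|---|---|---|---|---|---|
| 30 | 2% | 30/0.98 = 30.6 → 31 | 30/30 = 100% | 30/31 = 96.8% | 3.2 |
| 30 | 5.6% | 30/0.944 = 31.8 → 32 | 100% | 30/32 = 93.8% | 6.3 |
| 30 | 12% | 30/0.88 = 34.1 → 34 | 100% | 30/34 = 88.2% | 11.8 |
| 24 | 5.6% | 24/0.944 = 25.4 → 25 | 24/24 = 100% | 24/25 = 96.0% | 4.0 |
| 24 | 12% | 24/0.88 = 27.3 → 27 | 100% | 24/27 = 88.9% | 11.1 |

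Exact 95% intervals: 30/30, 88–100%; 30/32, 79–99%; 30/34, 73–97%. If 10% of the remaining 30 fail for other reasons (an assumption), 27/30 = 90% compares with 27/32 = 84% and 27/34 = 79%.

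The NAC-preservation series in section 1.1 kept the NAC in 61 of 112 patients (54.5%). Taken as f = 51/112 = 45.5%, it would give a shift of 45.5 points at s = 100%. It marks an outer limit and is not a forecast for this trial.

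These inputs fit loosely. Specimen involvement is not frozen-section positivity. Section 3 excludes lesions of 4 cm or more, extensive intraductal disease and shallow retroareolar lesions. The 12 to 18 in section 10.1 are patients who begin irradiation, not all frozen-negative operated patients.

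**Step 4: the direction is not general.** The upward shift applies to frozen-positive patients only. Patients positive on permanent section or at the margins had the NAC spared at operation. If success means technical completion, removing one of them takes one from both numerator and denominator: from 27/30 = 90.0% to 26/29 = 89.7%, a fall. If study patients meant everyone enrolled, including those never operated on, the rate would also fall.

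**Step 5: data capture.** Section 11.5 requires a case report form for treated patients but does not restrict forms to them, so it does not narrow section 9.0. Surgery is itself part of the section 4.0 treatment plan, and section 5.2 has the frozen-section result recorded.

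**The case for a change.** The best case for a change runs as follows. Section 10.2 uses a different term from 10.1 and does not cite it. Section 10.1 does not say whether an operation in which NAC-sparing was abandoned counts as surgery. The same patient can therefore be evaluable in one section and off study in another, and no sentence says which status 10.2 follows. If 10.1 was meant, a sentence would say so at almost no cost. The place of permanent-section and margin positives is also left open.

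Part of this stands. The cross-reference is missing, success is undefined, and the classification of those two groups is not stated. The rest does not carry. The doubt about the word surgery is thin, given where sections 4.1.1, 5.2 and 6.1.2 put the frozen section. Nothing in the protocol directs that a disposition label should define an analysis denominator.

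The preferred remedy also involves a choice of question. A rate among all patients taken to theatre measures how often the planned operation can be delivered. A rate among frozen-negative patients measures technical success where the operation was permitted. Both are legitimate, and treating permanent-section or margin positives as surgical failures is a preference that the plan does not have to share.

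**Conclusion.** The concern does not call for a change. Read with section 10.1, the denominator is all patients who undergo surgery, frozen-positive patients are included as non-successes, and the bias is zero. Only if an analyst ignored 10.1 and imported the screen-failure label would the rate be overstated, by about 3 to 12 points for 30 remaining patients under assumed shares of 2% to 12%. That range rests on background figures that do not closely match this trial.

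The rate is descriptive and has no part in dose finding, sample size or the stopping guidelines; surgical complications are monitored separately in section 10.3.3. In a study of this size an analyst would show the numbers operated on, frozen-positive and completed, and either rate could be read from them. This is a gap in detail that sensible analysis fills.

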## **10.3 Interim Monitoring**

### **10.3.1 Role of the Research Team and the DSMC**

The Research Team will continuously monitor study accruals and adverse events from both surgery and radiation treatment. In particular, for the purpose of escalation and de-escalation (section 4.2) patients will be monitored closely during the 30 days after completion of NAC radiation treatment, and subsequently for any toxicity or adverse reaction to treatment. All toxicities, regardless their grade, will be recorded in the patient case report form using NCI/CTEP Common Terminology Criteria for Adverse Events (CTCAE) version 3.0.

The Sylvester Comprehensive Cancer Center's Data and Safety Monitoring Committee (DSMC) will monitor this protocol according to the Cancer Center's DSM Plan. In its oversight capacity, the DSMC bears responsibility for suspending or terminating this study.

DSMC oversight of the conduct of this trial includes ongoing review of accrual and adverse event data. The guidelines appearing in Sections 10.3.2, and 10.3.3 are offered for DSMC consideration in assessing accrual, adverse events. In addition, the DSMC will review reports from all audits, site visits, or study reviews pertaining to this clinical trial and take appropriate action.

### **10.3.2 Safety: Early stopping due to radiation-related toxicity**

During the dose escalation/de-escalation for radiation dose-finding, there is no radiation-related toxicity that would suggest stopping the study early due to radiation-related toxicity beyond the dose escalation/de-escalation stopping rules described in section 4.2.5.

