**Dose level II: 25 Gy total (2.5 Gy for 10 fractions) (Starting Dose)**

Dose level III: 30 Gy total (3.0 Gy for 10 fractions)

Dose level IV: 35 Gy total (3.5 Gy for 10 fractions)

The patients will be receiving postoperative NAC irradiation using electrons **starting at Dose level II**. Dose levels will be escalated by 0.5 Gy per fraction for an overall 5 Gy increase per level up to 3.5 Gy per fraction and a total dose of 35 Gy. **Evaluable patients** will be defined as any eligible patient that begins NAC irradiation treatment.

DLT (dose-limiting toxicity), as defined in section 4.2.6, will be evaluated during radiation treatment period plus an **additional observation period of 30 days** following completion of NAC radiation.

We propose a **modification of standard dose-escalation design, treating cohorts of 2 to 6 patients per dose level of NAC irradiation**. The main features of the proposed escalation design is that (1) no more than 2 patients will experience DLT at a given radiation dose and (2) escalation to a higher dose occurs only after a cohort of 6 patients have been evaluated at a given radiation dose.

Dose escalation/de-escalation rules	
Number of patients with DLT at a given dose level	Escalation Decision Rule
0 or 1 out of 6 patients	Enter 6 patients at the next higher dose level.
2 out of 2 to 6 patients	Dose escalation stops. However, if the dose tested is dose level II, the starting dose level, then de-escalation occurs. In this case, dose level I will be tested in 2 to 6 patients.
The highest dose tested at which $\leq 1$ out of 6 patients experiences DLT will be declared the MTD and it will be the recommended phase II dose .	

Thus, as stated in the dose escalation/de-escalation rules above, if 0 or 1 patient experiences DLT (as defined in section 4.2.6) among 6 patients, the dose level will be judged to be acceptable. If this occurs, then a new cohort of 2 to 6 patients will be accrued at the next higher dose level. If 2 patients experience DLT among 2 to 6 patients at a given dose level, then the corresponding dose will be declared to be unacceptable. If the **starting dose level** (dose level II) proves to be unacceptable, then de-escalation occurs to dose level I and 2 to 6 patients will be enrolled at dose level I.

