The **maximum tolerated dose (MTD)**, among the doses tested, will be determined as the highest **NAC irradiation** dose level at which  $\leq 1$  out of 6 patients experiences DLT. The MTD will be declared the **“potential” recommended phase II dose (RP2D)** of post-operative prophylactic NAC irradiation after NAC-sparing mastectomy **with reconstruction** in patients with ductal carcinoma in-situ or invasive breast cancer.

**Simultaneous enrollment:** Simultaneous enrollment will be permitted under the following circumstance:

- If  $j$  ( $j \leq 4$ ) patients have been treated at a given dose and there are no DLTs, patients  $(j+1)$  and  $(j+2)$  may be enrolled simultaneously at the same dose level.

For instance, the first two patients could be enrolled simultaneously, that is, patient 2 could be enrolled within <30 days apart after patient 1 has completed the radiation treatment. As another example, If the first patient to receive a NAC radiation dose level does not experience DLT, within the DLT evaluation period of minimum 35 days, patients 2 and 3 may be enrolled simultaneously at the same dose level; that is, patient 3 can be enrolled before patient 2 has been fully evaluated for DLT within <30 days apart after patient 2 has completed the radiation treatment.

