#### **4.2.6 Definition of dose limiting toxicity (DLT)**

Dose limiting toxicity (DLT) is defined as any of the following toxicities occurring during radiation treatment period plus an **additional observation period of 30 days** following completion of NAC radiation:

- a) Grade 4 skin rash
- b) Grade 4 pain
- c) NAC necrosis
- d) Any toxicity requiring interruption of the NAC irradiation by > 2 weeks (14 calendar days), except if interruption is secondary to LINAC machine or unpredictable weather problems or unrelated medical conditions that would prevent the subject to come for treatment.
- e) Any grade 4 or 5 treatment-related toxicity

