#### **4.2.7 Expansion cohort**

An additional expansion cohort of 12 patients will be enrolled at the “**potential**” recommended phase II dose (RP2D) **to confirm its safety**.

If safety is confirmed in the total 18 patients (6 from dose-finding part of study plus 12 from the expansion cohort) treated at the “**potential**” (RP2D, the corresponding dose will be declared the **RP2D**).

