#### **Expansion cohort:**

An additional expansion cohort of 12 patients will be enrolled at the "potential" recommended phase II dose (RP2D).

If a radiation-related (possible, probable, or definite) death (grade 5 toxicity) occurs, enrollment will be suspended and continuation of the study will be reassessed by the DSMC.

Unacceptable radiation-related toxicity (possible, probable, or definite) is defined as grade 3, 4, or 5 adverse events, excluding grade 3 adverse events that resolve or down grade to grade 2 within 14 days.

Unacceptable radiation-related toxicity (possible, probable, or definite) is expected

to occur in no more than 10% of patients. If there is evidence that the true rate of this toxicity exceeds 20%, then the study should be suspended or possibly terminated early. Specifically, we suggest as a guideline for early termination a posterior probability of 90% or higher that the true rate exceeds 20%. The table below shows specific instances where this guideline is met, suggesting early termination, and due to evidence of excessive toxicity.

Number (%) of patients experiencing unacceptable radiation-related toxicity #	Total patients evaluated
3	3 to 5
4	6 to 9
5	10 to 12

#:Radiation-related toxicity (possible, probable, or definite) is defined as grade 3 or higher adverse events, excluding grade 3 adverse events that resolve or down grade to grade 2 within 14 days.

To illustrate the stopping guidelines, suppose that 5 evaluable patients in the expansion cohort have been assessed for radiation-related toxicity and 3 of them have experienced grade 4 unacceptable toxicity. (See row 1 of the above table.) Under this circumstance, the observed rate of unacceptable toxicity is 60%, resulting in a posterior probability of 92.7% (not shown) that the true underlying rate exceeds 20%, thereby suggesting early termination.

Posterior probabilities for the above table are calculated under a weak prior beta distribution with parameters  $\beta_1 = 0.2$  and  $\beta_2 = 1.8$ , which corresponds to an expected unacceptable radiation-related toxicity rate of 20% based on very limited information, roughly equal to having studied 2 patients. This prior distribution implies also a priori chance of only 18% that true rate is 20% or greater.

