### 10.3.3 Safety: Early stopping due to surgery-related toxicity

We propose the following guidelines for the DSMC in its review of accumulating data on surgery-related toxicity. These guidelines were developed using Bayesian methods, which can be applied at any stage of enrollment without pre-specification of the number of interim analyses to be performed, or the number of patients evaluable for toxicity or survival at the time such assessments are made (26,27). Under the Bayesian method, we assign a prior probability (level of belief at the start of the trial) to a range of possible values for the true rate. As data on treated patients become available, this probability distribution is revised and the resulting posterior probability becomes the basis for recommending either early termination or continuation of the study. In the sections that follow, we provide specific stopping guidelines based on posterior probabilities for interim monitoring of surgery-related toxicity over the course of this trial. Underlying assumptions for the prior distribution are also presented.

If a surgery-related (possible, probable, or definite) death (grade 5 toxicity) occurs, enrollment will be suspended and continuation of the study will be reassessed by the DSMC.

Unacceptable surgery-related toxicity (possible, probable, or definite) includes grade 3-4 bleeding, infection, NAC necrosis, and any unexpected grade 3.

Unacceptable surgical-related toxicity (possible, probable, or definite) is expected to occur in no more than 10% of patients. If there is evidence that the true rate of this toxicity exceeds 20%, then the study should be suspended or possibly terminated early. Specifically, we suggest as a guideline for early termination a posterior probability of 90% or higher that the true rate exceeds 20%. The table below shows specific instances where this guideline is met, suggesting early termination, and due to evidence of excessive toxicity.

Number (%) of patients experiencing unacceptable surgery-related (possible, probable, or definite) toxicity	Total patients evaluated
3	3 to 5
4	6 to 9
5	10 to 12
6 (55 to 60%)	13 to 16
7	17

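### During dose finding, a radiation-related death counts as one ordinary DLT and the written rule can still escalate; the same death in the expansion cohort suspends enrolment

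*Combined protocol and SAP*

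**What the plan says.** - **Section 4.2.6(e)** lists "Any grade 4 or 5 treatment-related toxicity" among the DLTs. The window is the radiation period plus 30 days. A death has the same weight as any other DLT.
- **Section 4.2.5** states that "if 0 or 1 patient experiences DLT (as defined in section 4.2.6) among 6 patients, the dose level will be judged to be acceptable", and the next higher dose then opens. Escalation stops only at two DLTs. The highest tested dose with at most one DLT in six becomes the MTD. There is no exception for a fatal DLT.
- **Section 4.2.7** then enters 12 more patients at that dose.
- **Section 10.3.2, dose-finding paragraph**, says that "there is no radiation-related toxicity that would suggest stopping the study early due to radiation-related toxicity beyond the dose escalation/de-escalation stopping rules" of 4.2.5.
- **Section 10.3.2, under the expansion cohort heading**, says: "If a radiation-related (possible, probable, or definite) death (grade 5 toxicity) occurs, enrollment will be suspended". The DSMC then reassesses whether the study continues.
- **Section 10.3.3** has the parallel surgical rule: "If a surgery-related (possible, probable, or definite) death (grade 5 toxicity) occurs, enrollment will be suspended". It is not limited to one part of the study.

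**The concern.** The plan has a clear rule for a treatment-related death: stop enrolling and have the DSMC look. It applies that rule to surgical deaths throughout and to radiation deaths in the expansion, where the dose has already passed dose finding. It does not apply it to radiation deaths during escalation, where least is known about each dose. There, 10.3.2 is not merely silent; it says that nothing beyond the DLT count suggests stopping. Followed to the letter, patients could receive a higher dose, or 12 more could receive the same dose, after a fatal radiation toxicity and without a required review.

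**Working it through.** **1. Does the rule weight all DLTs equally?** Section 10.1 gives two operating characteristics for six patients. Exact binomial calculation for the rule that escalates on 0 or 1 DLT:

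- P(not escalating | 35%) = 1 − 0.65^6 − 6 × 0.35 × 0.65^5 = 0.681 (stated 68%).
- P(escalating | 20%) = 0.80^6 + 6 × 0.20 × 0.80^5 = 0.262 + 0.393 = 0.655 (stated 66%).

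Both figures reproduce. The plan's own numbers therefore rest on a simple count, with no separate treatment of a death. At a 20% rate, 0.393 / 0.655 = 60% of escalations happen with exactly one DLT, which the rule allows to be a death.

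**2. What does the rule do after one death?** The dose is acceptable if the other five patients have no DLT. With independent patients and DLT rate p, that probability is (1 − p)^5:

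| Assumed p | (1 − p)^5 |
|---|---|
| 5% | 0.774 |
| 10% | 0.590 |
| 20% | 0.328 |
| 35% | 0.116 |

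The 20% and 35% rates are the examples in 10.1; the other two are assumptions. These probabilities are conditional on a death having occurred.

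**3. What follows if the dose is acceptable?**

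- Level II or III: the next higher dose opens.
- Level IV: there is no higher dose, so level IV becomes the MTD and the 12 expansion patients enter at it.
- Level I, reached only after level II has failed: level I becomes the MTD and again leads to the expansion.

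**4. How much time is there for someone to intervene?** Paired enrolment is allowed only while "patients have been treated at a given dose and there are no DLTs", so after a death the later patients at that dose enter one at a time, at no less than 35 days each (10.1). With pairs 1-2, 3-4 and 5-6:

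- Death in patient 1 or 2: 4 × 35 = 140 further days at that dose, at least.
- Death in patient 3 or 4: 2 × 35 = 70 days, at least.
- Death in patient 5 or 6: no further patient is due at that dose once the pair has been evaluated.

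Other permitted pairings change these figures. With pairs 2-3 and 4-5, a death in patient 2 leaves 3 × 35 = 105 days and one in patient 4 leaves 35.

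**5. Which patients does the radiation death rule cover?** The 12 expansion patients, out of 12 + 12 = 24 to 18 + 12 = 30 planned: 12/24 = 50% to 12/30 = 40%. It covers none of the 12 to 18 in dose finding.

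**6. Late deaths.** A radiation-related death more than 30 days after treatment is outside the DLT window and does not count even as one DLT, so the gap is slightly wider than steps 2 and 3 show.

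**The case against.** The strongest reply is that the gap is almost empty. Radiation is given in weeks 5 to 8 after mastectomy with reconstruction, and the surgical rule applies to any death even possibly related to surgery. Sections 6.1 and 6.2 list infection and death as risks of surgery and reconstruction; section 6.3 lists neither for radiation. Treatment is superficial electrons. Most plausible fatal routes would be hard to call not even possibly surgical, and 10.3.3 would then suspend enrolment. This stands: it makes the event rare and narrows the case.

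The second reply is that oversight exists anyway. Serious and fatal events go to the principal investigator within 24 hours and to the IRB promptly, within ten working days at most. The DSMC reviews adverse events and can suspend the study. Section 10.3.1 presents 10.3.2 and 10.3.3 as guidance for the DSMC to weigh, so the contrast between mandatory and discretionary is softer than the word *will* suggests. At no more than six patients a year, four further patients would take about eight months (4/6 of a year). The expansion dose is only a potential recommended dose until safety is confirmed in all 18 patients, so the death stays in the final judgement. The Cancer Center's DSM Plan, which is not in the documents, may itself require a pause.

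All of this is fair, but none of it puts a required pause into this protocol. The guidance handed to the DSMC for dose finding says that nothing beyond the DLT count suggests stopping, and a late judgement on 18 patients does not protect the 12 who enter after the death. The plan did not rely on general DSMC authority for surgical or expansion deaths.

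**Conclusion.** The concern holds. As written, a dose-finding death judged radiation-related and not even possibly surgery-related is at most one DLT. The dose is then still judged acceptable with probability 77% to 12% over assumed DLT rates of 5% to 35% in the other five patients. Those figures assume independent patients and a death within the DLT window; they say nothing about how often a death would occur, which should be very seldom. No estimate, sample size or analysis is affected. The defect is a missing mandatory pause in the part of the trial with the least dose information. It should be fixed because the consequence is grave and the remedy already exists in the plan. Whether the DSM Plan supplies a pause cannot be seen from these documents; if it does, the dose-finding sentence in 10.3.2 still needs correcting to agree with it.

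**What to change.** Move the grade 5 sentence in 10.3.2 to the start of that section, above the dose-finding paragraph and the expansion heading, so that any radiation-related death at any dose level suspends enrolment until the DSMC has reassessed the study. The sentence carries no time window, so it would also cover deaths after the 30-day DLT period. Then amend the dose-finding paragraph so that it refers to the rules in 4.2.5 and the grade 5 rule above.

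The DLT count in 4.2.5 and both toxicity tables in 10.3 stay as they are. The cost is one sentence moved and one amended, with no new patients, data or analyses. The only downside is a possible short pause in accrual after a death, which the plan already accepts for surgical deaths and for the expansion cohort.
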